4. Confirm that platelet-rich plasma is a procedure **safe** through the systematic recording of adverse effects and complications associated with its use.

Materials and methods

Design

Randomized controlled clinical trial, with intervention group and control group, usual treatment, blind for the treatment received by the patient and for clinical and radiological evaluation.

Scope

The entire study will be carried out at the Hospital Italiano de Buenos Aires headquarters.

Schedule - masking - intervention

Stage 1: All patients with rotator cuff tendinopathy, clinically diagnosed and confirmed by MRI, will be invited to participate in this study.

After confirming that the patient meets the inclusion criteria, the study will be explained in detail through the informed consent process (See Consent Annex 1).

Stage 2: Once the patient agrees to participate and has signed the informed consent, they will be randomized (see randomization).

To the patients of group **1:** (control) a subacromial infiltration with corticosteroids (betamethasone 2 mg) will be performed under ultrasound control.

To the patients of group **2:** (Intervention) a subacromial infiltration with PRP will be performed under ultrasound control.

The week prior to the infiltration, all patients will undergo a prior ultrasound to confirm rotator cuff tendinopathy and rule out associated supraspinatus ruptures.

Masking of patients:

At the time of blood collection, patients will be placed in a hemotherapy extraction chair with a screen that will prevent the patient from seeing their arm at the time of blood collection. All patients will have a local anesthetic (cutaneous lidocaine) placed in the crease of the elbow at the extraction site. The patients in the intervention group will be injected with the extraction needle and 20 ml of blood will be obtained for the preparation of the PRP.

On the other hand, the patients in the control group (corticosteroid) will be given anesthetic and a dermal micro-puncture will be performed with the vacutainer simulating blood extraction. After this, they will wait 1 minute, simulating the time it takes for the extraction bag to fill with 20 ml.

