1. Adults between 18 and 50 years with rotator cuff tendinopathy.

Selection criteria

Inclusion criteria

1. Adults between 18 and 50 years old with rotator cuff tendinopathy defined as clinically compatible and confirmed by ultrasound.
2. At least 3 months of failed conservative treatment (decreased activity, anti-inflammatories, kinesiology for at least 3 months before diagnosis).

Exclusion criteria

1. Refusal to participate or informed consent,
2. previous shoulder surgery,
3. Partial or total tears of the rotator cuff,
4. Patients with shoulder osteoarthritis > 2 according to the Samilson and Prieto classification
5. Advanced fatty infiltration of the rotator cuff muscles (STAGE 3 or 4 according to Goutallier)³²
6. Systemic or rheumatoid arthritis,
7. uncontrolled diabetes,
8. Acute or chronic infections of the shoulder to be operated on
9. Ongoing cancer chemotherapy therapies
10. Sepsis, septic arthritis, osteomyelitis or other ongoing infectious processes;
11. Patients with autoimmune diseases;
12. pregnant,

Eligible patients will be enrolled in the study by giving their informed consent.

Preparation of platelet-rich plasma

For the PRP group, a leukocyte-poor preparation from a prepackaged kit (RegenLab, Lausanne, Switzerland) will be used. According to the manufacturer's manual, 10 ml of venous blood will be drawn into a blood collection tube containing a sodium citrate anticoagulant and a proprietary separating gel (thixotropic gel) to isolate the red and white blood cells from the PRP. Samples will be centrifuged at 1500g for 5 minutes to produce approximately 7 mL of 80% platelets at 1.6x concentration. The manufacturer reports a filtration of 99.7%, 87 to 89%, 70 to 75%, and 96.5% of red blood cells, white blood cells, mononuclear cells, and granulocytes, respectively. The supernatant is then resuspended by inverting the tube several times and withdrawn into a separate 5 mL syringe for subacromial injection.

This procedure will be performed 2 times in each patient. The product from the first kit will be injected into the patient. Instead, the product from the second kit will be used to evaluate the final composition of the PRP. These specific measurements will include: the final average of platelets, leukocytes and erythrocytes, and the specific formula of leukocytes and growth factors. This will allow us to establish a correlation between the specific composition of the PRP and the functional results of the patient.

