To calculate the sample size, the expected values of the variable "pain" represented by the VAS, which is the main outcome variable, are used. The minimal clinically relevant difference (MCID) was previously described in the setting of rotator cuff disease as 1.5 points with a standard deviation of 2.41 points on a 10-point scale for shoulder pain.²² We will work with a type I error probability of 5% and a power of 90%. Using these parameters in a superiority formula, a sample size of 45 patients per group was calculated. Considering the possibility of a loss to follow-up of 10% of the patients per group, 50 patients per group will be included, with a total final sample of 100 patients. The sample size was calculated using the formula of Fleiss et al.²³

Randomization

All included patients will be randomized after obtaining informed consent. Each patient will be randomly assigned a treatment arm using the online randomizer (<http://protocolos.hospitalitaliano.org.ar>) to treatment arms 1 (control) or 2 (intervention)

ethical considerations

Participation in the study will be in all cases voluntary and certified by the informed consent process. The study will be carried out in full accordance with current national and international regulations: Declaration of Helsinki of the World Medical Association, Provision 6677/10 of ANMAT, and the Standards of Good Clinical Practices ICH E6.

The proposed intervention does not frequently present adverse events and there are known contraindications for its application. The procedure will be paid for by the financing of the study, it will not imply any cost to the patient or their health coverage. The costs of monitoring and periodic evaluations will be borne by the study investigators.

All study data will be treated with the utmost confidentiality, with restricted access only to authorized personnel for the purposes of the study in accordance with current legal regulations National Law on Protection of Personal Data 25,326 (Habeas Data Law).

Damage or complications

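### Randomisation is tied to signed consent, while baseline scoring and the week-before ultrasound are dated only from infiltration, so either may be done after allocation with the arm known

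*Combined protocol and SAP*

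**What the plan says.** All references are to the combined protocol and SAP.

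- **Time of randomisation.** Stage 2 (Schedule - masking - intervention): "Once the patient agrees to participate and has signed the informed consent, they will be randomized (see randomization". Randomization section: "All included patients will be randomized after obtaining informed consent". Neither names another step that must come first.
- **Eligibility before consent.** Stage 1: "After confirming that the patient meets the inclusion criteria, the study will be explained in detail through the informed consent process". Selection criteria: "Eligible patients will be enrolled in the study by giving their informed consent". Inclusion criterion 1 requires "rotator cuff tendinopathy defined as clinically compatible and confirmed by ultrasound", without saying which examination or when. Tears of the cuff are exclusion criterion 3.
- **Ultrasound.** Stage 2: "The week prior to the infiltration, all patients will undergo a prior ultrasound to confirm rotator cuff tendinopathy and rule out associated supraspinatus ruptures". The imaging paragraphs under Variables to be measured give this scan two purposes: to confirm the tendinopathy, and to exclude tears, including progression to a partial tear.
- **Baseline scoring.** Variables to be measured assigns mobility, pain, ASES, Constant and Pittsburgh to the principal investigator, 24-48 hours before infiltration. Masking of patients has the same person inject the assigned treatment.
- **Blinding.** The Design paragraph calls the trial "blind for the treatment received by the patient and for clinical and radiological evaluation", with no visit named. The procedures name blinded assessors only for follow-up: the shoulder fellow for the scores and the sonographer for the post-infiltration scan.
- **Analysis.** The statistical section does not say whether follow-up values, change or baseline-adjusted values are compared, and it defines no analysis population. The hypothesis speaks of greater improvement.

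**The concern.** Two steps that should not depend on the arm have no stated position relative to allocation.

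The first is baseline scoring. The arm may be generated at consent, and the baseline visit takes place one to two days before the injection. The person scoring that visit could then already know what they will inject. Goniometer mobility and the mobility part of Constant rest on the assessor's measurement, so they could shift with the arm. A shifted baseline carries straight into a change score and partly into a baseline-adjusted comparison.

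The second is the tear check. If the week-before scan follows allocation, a patient could be declared ineligible by someone who knows the arm. Such exclusions need not be balanced between arms, and the plan does not say whether those patients stay in the analysis.

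**Working it through.** **1. Order of events, from the text**

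| Step | Anchored to | Placed before allocation? |
|---|---|---|
| Inclusion criteria confirmed (Stage 1) | Before consent | Yes |
| Randomisation (Stage 2; Randomization) | After consent | – |
| Week-before ultrasound (Stage 2; Variables) | Infiltration | Not stated |
| Baseline scoring (Variables) | Infiltration | Not stated |
| Disclosure of the arm | Nothing | Not stated |

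The interval from consent to infiltration is not given either. The gap is certain for baseline scoring, because no sentence ties it to allocation. For the ultrasound it depends on whether the week-before scan is the one meant in inclusion criterion 1.

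**2. Inputs for size**

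The plan gives no figure for this point. From Sample size: minimal clinically important difference 1.5 points, SD 2.41, 50 per group less 10% loss = 50 × 0.90 = 45 per group. The tear rate, the baseline shift and the baseline correlation are not in the documents and are assumed below. Type I error is two-sided at nominal 5%, from the noncentral t distribution, with true effect zero.

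**3. Primary VAS: exclusions in one arm only (unfavourable case)**

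Bias = p × d, where p is the share excluded in one arm and d is how much worse the excluded patients would have scored than those retained. SE = 2.41 × √(1/45 + 1/[45(1 − p)]).

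| p | d | Bias (points) | SE | Bias/SE | Type I error |
|---|---|---|---|---|---|
| 0.05 | 1.5 | 0.075 | 0.515 | 0.146 | 5.2% |
| 0.10 | 1.5 | 0.150 | 0.522 | 0.287 | 5.9% |
| 0.05 | 3.0 | 0.150 | 0.515 | 0.291 | 6.0% |
| 0.10 | 3.0 | 0.300 | 0.522 | 0.575 | 8.8% |

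The first two rows are 0.075/1.5 = 5% and 0.15/1.5 = 10% of the minimal clinically important difference.

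**4. Assessor-measured variables: arm-related baseline shift s**

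- *Change analysed, s in SD of change.* SE = √(2/45) = 0.211. For s = 0.1: 0.1/0.211 = 0.47, type I error 7.6%. For s = 0.2: 0.2/0.211 = 0.95, type I error 15.5%.
- *Baseline-adjusted, s in per-visit SD, correlation r = 0.5.* Bias = r × s; residual SD = √(1 − 0.5²) = 0.866; SE = 0.866 × 0.211 = 0.183. For s = 0.1: 0.05/0.183 = 0.27, type I error 5.8%. For s = 0.2: 0.10/0.183 = 0.55, type I error 8.4%.
- *Follow-up values alone.* Baseline does not enter, so the effect is 0.

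At r = 0.5 the SD of change is √(2 − 2r) = 1 per-visit SD, so the two sets are on the same scale. These figures suit a variable measured wholly by the assessor, such as goniometer mobility. Applied to the whole Constant score they would overstate the effect, since only part of that score is assessor-measured.

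**The case against.** The strongest reply concerns the ultrasound. Only one pre-infiltration ultrasound is described anywhere, and its first purpose, confirming the tendinopathy, matches inclusion criterion 1. Stage 1 confirms the inclusion criteria before consent, and only eligible patients are enrolled. Read together, this puts the scan before consent and so before randomisation. Its place after randomisation in the Stage 2 text proves little, since it also follows the sentences on the injections and is itself described as prior. This reading is fair and may be what is intended. It is not stated, however: Stage 1 refers to confirmation by MRI ("All patients with rotator cuff tendinopathy, clinically diagnosed and confirmed by MRI, will be invited to participate in this study"), its check names the inclusion criteria whereas tears are an exclusion criterion, and the scan is timed from infiltration. The tear-exclusion risk therefore stands only conditionally.

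The second reply is that the Design line makes clinical and radiological evaluation blind with no visit excepted, and that injecting later does not show knowledge of the arm a day or two earlier. Both points are correct. A reader might infer from the plan that the principal investigator scores baseline unblinded, or that eligibility is checked only after randomisation. The documents support neither. What remains is that no procedure carries the Design line's blinding to the baseline visit, and that the baseline scorer must learn the arm at some unstated time before injecting.

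The third reply is that the main outcome is barely touched, because VAS is rated by a blinded patient. This also stands. The larger error rates need three things together: the arm known at baseline, a shift of the assumed size, and an analysis of change that the plan does not specify. Mobility is not a named objective in its own right.

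**Conclusion.** The concern holds as a gap in the order of steps. Baseline scoring can, as written, follow allocation with the arm known. A tear exclusion can do so too, unless the week-before scan is the ultrasound of inclusion criterion 1. No unblinding and no selective exclusion is documented.

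Severity is minor to moderate. For the primary VAS, the assumed one-arm exclusion of 5% or 10% with a 1.5-point difference gives a bias of 0.075 or 0.15 point and type I error of 5.2% or 5.9%. For assessor-measured variables, an assumed shift of 0.1 or 0.2 SD gives type I error of 7.6% or 15.5% if change is analysed, 5.8% or 8.4% with baseline adjustment at correlation 0.5, and no effect if follow-up values alone are compared. All these rates and shifts are assumptions; the documents supply none. The point is still worth acting on because the remedy is cheap, and a baseline taken or a patient excluded with the arm known is hard to repair afterwards.

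**What to change.** Amend Stage 2 and the Randomization section so that allocation is generated and released only after (1) the week-before ultrasound has confirmed eligibility and (2) baseline VAS, ASES, Constant, Pittsburgh and mobility are locked in the database, for example on the day of infiltration before blood collection. Consent can stay where it is. State that all patients randomised from that point are analysed as allocated.

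If randomisation stays at consent, state that the arm is concealed from the baseline scorer and the sonographer until both steps are complete.

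Cost: a reordering of existing steps, with no new visit, staff or test. The downside is that the arm is known only shortly before the procedure, so the product has to be prepared then. The plan already describes blood collection, 5 minutes of centrifugation and injection as successive steps. The concealment alternative needs only a restriction on who can see the allocation.

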Variables to be measured and data documentation

All the variables to be measured will be recorded in a RedCap database specially designed for this clinical trial.

A) Demographic and related to the injury.

They will be recorded by the principal investigator 24-48 hours prior to the infiltration.

- Sex: male - female
- Age: Age in years on the day of infiltration
- Smoking: yes-no

B) Cynic variables

Pre-infiltration evaluation: It will be in charge of the principal investigator and it will be carried out 24-48 hours before the infiltration in the orthopedics office.

In it will be evaluated:

clinical variables: Mobility - Pain - Functional Scores (ASES - Constant) - Sleep disorders (Pittsburgh Score)

Imaging variables: Chronic tendinopathy will be defined as the presence of a hyperintense signal in the supraspinatus on magnetic resonance imaging (carried out a maximum of 6 months prior to clinical diagnosis), with the absence of partial or total ruptures of the tendon or as the presence of a hyperechoic signal in the supraspinatus. supraspinatus with increased intratendon Doppler flow. The presence of the tendinopathy will be confirmed by ultrasound the week prior to the infiltration to rule out the progression of the tendinopathy to a partial rupture of the tendon and to evaluate the presence of flow within the supraspinatus as a sign of tendinopathy with echodoppler.

Post-infiltration evaluation:

In it will be evaluated:

clinical variables: Mobility - Pain - Functional Scores (ASES - Constant) - (Pittsburgh Score) at one month, 3 months and 6 months postinfiltration. It will be in charge of the Shoulder Fellow who will not know to which branch of treatment the patient was assigned. That is to say it will be *blinded to intervention*.

Imaging variables: The presence of vascular flow within the tendon will be measured in the musculoskeletal ultrasound 6 months after the infiltration in the usual way. It will be in charge of a doctor specialized in musculoskeletal ultrasound who does not will know to which treatment arm the patient was assigned. That is to say it will *beblinded to intervention*.

The variables that will be evaluated are described below:

- Mobility: *The 4 mobility parameters will be measured in degrees with a goniometer*
 - Anterior flexion
 - Abduction
 - External Rotation with the arm at 90⁰of abduction
 - Internal Rotation with the arm at 90⁰of abduction

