- Pain: The visual analogue scale (VAS) will be used to assess the level of pain during activities of daily living. 0 will be considered as "absence of pain" and 10 as "the worst pain of your life".
- General function of the shoulder: The ASES (American Shoulder and Elbow Surgeons) score will be used.¹⁵ (*Annex 2*) and Constant's score¹⁶ (*Annex 3*) Both scores evaluate the general functionality of the shoulder in different activities of daily living, the global mobility of the shoulder, and pain with usual tasks. They are scores ranging from 0 to 100. Both scores are validated and are the reference scores for clinical research on rotator cuff pathology.^{15,16}
- Sleep disorders: The Pittsburgh score will be used.²⁰ (*Annex 4*)

c) Imaging variables

- Magnetic resonance imaging (MRI) of the affected shoulder:

The preinfiltration MRI will measure the presence of pathological hyperintensity in the supraspinatus, in the absence of partial or total tears of the rotator cuff.

The resonance must have been performed a maximum of 6 months prior to the clinical diagnosis of the tendinopathy. Otherwise it will be repeated.

Ultrasound 1 week before infiltration and 6 months after infiltration:

The shoulder musculoskeletal ultrasound that will be performed on all patients 1 week before infiltration will confirm the diagnosis of cuff tendinopathy and the absence of partial or total cuff tears. In addition, an echodoppler will be performed to determine the presence of intratendinous flow as a manifestation of tendinopathy. In the post-infiltration control musculoskeletal ultrasound 3 months after the infiltration, tendon healing will be evaluated, which will be defined as the absence of intratendinous vascular flow. Both MRI and ultrasound are part of the study and routine follow-up of patients treated for rotator cuff tendinopathy.

d) Variables related to security

Adverse effects and immediate post-infiltration complications, one month, 3 months and 6 months post-infiltration will be recorded.

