In the event that the patient presents a complication, they will have the contact number of the principal investigator to be attended by him or by a surgeon from the team in the orthopedic clinics or on duty at the Italian Hospital of Buenos Aires. Likewise, the doctors on duty will be informed about the development of the following protocol in order to notify the principal investigator or a member of the team in the event that a patient presents any post-infiltration complication.

Scheme of the evaluation points in time, responsible for the evaluation and the variables that will be recorded

	pre-infiltration (24-48 hours prior)	1 month post-infiltration	3 months post-infiltration	6 months post-infiltration
Evaluator	Principal investigator	Shoulder Fellow	Shoulder Fellow (clinical variables) Sonographer (imaging variables)	Shoulder Fellow (clinical variables)
Variables Clinics	-Demographic -Mobility -Pain -Functional Scores (ASES – Constant - Pittsburgh)	-Mobility -Pain -Functional Scores (ASES – Constant-Pittsburgh) -complications	-Mobility -Pain -Functional Scores (ASES – Constant-Pittsburgh) -complications	-Mobility -Pain -Functional Scores (ASES – Constant-Pittsburgh) -complications
Imaging variables	Magnetic nuclear resonance Ecodoppler musculoesquelético		Ecodoppler musculoesquelético	

Statistical analysis raised

Quantitative variables will be presented as mean and standard deviation or median and interquartile interval according to the observed distribution. Categorical variables will be presented as proportions. The 95% confidence intervals will be calculated for each of the estimators.

The comparison of continuous data between two groups will be analyzed with the t test if the distribution of the variables is normal or with the Mann-Whitney-Wilcoxon test if it is not. The analysis of categorical data will be carried out with the chi-square test. Statistical analysis will be performed with STATA MP version 16 (Stata Corporation, College Station, TX). A p value less than 0.05 will be considered statistically significant.

Sample size

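### Tendon healing has two conflicting assessment dates (3 and 6 months), and its definition would count as healed any patient who had no Doppler flow to begin with

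*Combined protocol and SAP*

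**What the plan says.** All places below are in the combined protocol and SAP.

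**Date of the follow-up Doppler**
- Post-infiltration evaluation, Imaging variables: vascular flow "will be measured in the musculoskeletal ultrasound 6 months after the infiltration in the usual way".
- Section c) Imaging variables, ultrasound sub-heading: "Ultrasound 1 week before infiltration and 6 months after infiltration".
- The paragraph directly under that sub-heading: "In the post-infiltration control musculoskeletal ultrasound 3 months after the infiltration".
- Scheme of the evaluation points in time: the sonographer and the follow-up Doppler appear only in the 3-month column. The 6-month column lists the Shoulder Fellow and clinical variables only.

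**Definition of healing**
- Section c) Imaging variables: "tendon healing will be evaluated, which will be defined as the absence of intratendinous vascular flow". Baseline flow is not mentioned.

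**Flow at entry**
- Schedule - masking - intervention, Stage 1: "All patients with rotator cuff tendinopathy, clinically diagnosed and confirmed by MRI, will be invited to participate in this study".
- Inclusion criterion 1: "rotator cuff tendinopathy defined as clinically compatible and confirmed by ultrasound". Flow is not named.
- Pre-infiltration evaluation, Imaging variables: chronic tendinopathy is the "presence of a hyperintense signal in the supraspinatus on magnetic resonance imaging" without rupture, or, as an alternative, a hyperechoic supraspinatus with increased Doppler flow.
- Section c) Imaging variables: the pre-injection ultrasound confirms the diagnosis, and a Doppler is then added to determine whether flow is present.

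**Analysis**
- The statistical analysis section gives a chi-square test for categorical data, with no rule for patients who have no flow at baseline.

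**The concern.** Two things are left open for the plan's only follow-up imaging outcome.

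First, staff cannot tell from the text when to scan. Different patients could be scanned at different times, or the healing time point could be settled after data have been seen.

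Second, healing should describe a change, but the definition looks only at the follow-up scan. A patient with no flow at either scan has not changed and would still be a success. Such patients add the same successes to both arms in expectation, which raises both healing rates and pulls them together. The Introduction contrasts PRP with corticosteroids on tendon regeneration, so a diluted or wrongly dated healing result would bear on the trial's rationale, although it does not touch the primary pain outcome.

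**Working it through.** **1. Date.** Set side by side, the statements split two against two.

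| Place | Follow-up Doppler |
|---|---|
| Post-infiltration evaluation, Imaging variables | 6 months |
| c) Imaging variables, ultrasound sub-heading | 6 months |
| c) Imaging variables, paragraph under that sub-heading | 3 months |
| Evaluation schedule | 3 months |

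The conflict does not come from a broken table, because the prose gives 3 months independently of it, directly beneath a sub-heading that gives 6.

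**2. Is flow required at entry?** Inclusion criterion 1 asks for ultrasound confirmation, and the only ultrasound definition in the plan includes increased Doppler flow; read together, these could require it. Against that, Stage 1 invites patients on MRI confirmation, the tendinopathy definition accepts MRI signal as an alternative, the added Doppler treats flow as something to be found out, and no inclusion or exclusion criterion names flow. The text supports either reading.

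**3. Effect of the definition.** The plan gives no healing rates and no share of patients without baseline flow, so there is no stated figure to reproduce. Inputs:
- n = 45 evaluable per arm (Sample size section).
- Two-sided 5% chi-square test. The 5% level and the test are in the plan; two-sided is assumed.
- Healing among patients with baseline flow: p₁ = 60%, p₂ = 30% (assumed).
- f = share of each arm with no flow at either scan (assumed, varied).

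Formulas:
- Observed rate in an arm = f + (1 − f)p.
- Observed difference = (1 − f)(p₁ − p₂).
- Power = Φ{[d − 1.96·√(2p̄(1 − p̄)/n)] / √([r₁(1 − r₁) + r₂(1 − r₂)]/n)}, where r₁ and r₂ are the observed rates, d their difference and p̄ their mean.

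Example, f = 0.2:
- r₁ = 0.2 + 0.8 × 0.6 = 0.68, r₂ = 0.2 + 0.8 × 0.3 = 0.44, d = 0.24, p̄ = 0.56.
- Power = Φ[(0.24 − 1.96 × 0.1046)/0.1015] = Φ(0.34) = 63%.
- Restricted to patients with baseline flow, n = 45 × 0.8 = 36 and d = 0.30: power = Φ[(0.30 − 1.96 × 0.1173)/0.1118] = Φ(0.63) = 73%.

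| f | Observed rates | Difference (points) | Power, all patients (n = 45) | Power, baseline flow only (n per arm) |
|---|---|---|---|---|
| 0 | 60% v 30% | 30 | 82.8% | 82.8% (45) |
| 0.05 | 62% v 33.5% | 28.5 | 78.2% | 80.7% (42.75) |
| 0.1 | 64% v 37% | 27 | 73.4% | 78.5% (40.5) |
| 0.2 | 68% v 44% | 24 | 63.4% | 73.5% (36) |
| 0.4 | 76% v 58% | 18 | 44.2% | 60.6% (27) |

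**4. Sensitivity.**
- Other healing rates at f = 0.2: 70% v 40% gives 66.5% in all patients against 73.5% restricted; 50% v 25% gives 47.5% against 59.4%. The last case starts from only 69% at f = 0.
- If 20% of no-flow patients develop flow (60% v 30%), the observed rates are 64% v 40% at f = 0.2 and 68% v 50% at f = 0.4, with all-patient power of 63% and 41%.
- Exact enumeration of the chi-square test at 60% v 30%, all patients, gives 81.8%, 72.2%, 62.4% and 45.7% at f = 0, 0.1, 0.2 and 0.4, within 2 points of the approximation.

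**The case against.** The date conflict has one possible defence: no sentence says there is only one follow-up scan, so the plan might intend flow at 6 months and healing at 3. That is the less likely reading, since neither the sub-heading nor the schedule lists both. It stands to this extent: the sponsor should say how many scans are intended.

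The case against the second part is stronger. Ultrasound confirmation is needed for entry, and the plan's only ultrasound definition includes increased flow. Flow is also described as a sign of tendinopathy, and the word healing presupposes something to heal. On that reading f = 0 and the definition does no harm. This cannot be ruled out, but the alternative MRI route and the separate Doppler step prevent it from being the settled meaning. An ambiguity of this kind is itself a reason to clarify.

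Three further points stand and limit the weight:
- Every input on healing rates and f is assumed, and nothing in the plan supports a value as high as 0.4. At f = 0.05 and 0.1, restriction recovers only about 2.5 and 5 points of power.
- Because the arms are randomised, the effect is dilution; it does not create a difference in expectation where there is none.
- Healing appears in none of the objectives, and the sample size rests on VAS. The pre-injection Doppler is already planned, so a restricted analysis would remain possible later, though it would then not be pre-specified.

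**Conclusion.** The concern holds. The 3- against 6-month conflict is plain on the face of the current text, and the plan cannot be followed as written until it is reconciled. The definition problem is conditional: it has an effect only if some enrolled patients have no baseline flow, which the plan neither requires nor excludes clearly. The difference then shrinks by the factor (1 − f), whatever the healing rates. On the assumed 60% v 30%, the power loss relative to f = 0 is about 9 points at f = 0.1 and 19 at f = 0.2; analysing only patients with baseline flow gives back about 5 and 10 of these. The sponsor should correct this, but it does not threaten the primary VAS result.

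**What to change.** 1. Reconcile the post-infiltration evaluation text, the ultrasound sub-heading and paragraph in section c), and the evaluation schedule to one follow-up Doppler time used for every patient. If two scans are in fact intended, schedule both and name the one that defines healing.
2. State whether baseline Doppler flow is an entry condition, and make Stage 1, inclusion criterion 1 and the imaging definition of tendinopathy agree.
3. If flow is not required at entry, define healing as flow present at the pre-injection Doppler and absent at follow-up. Analyse it in patients with baseline flow, and report new flow in the others separately.

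The cost is wording only: the pre-injection Doppler and a follow-up Doppler are already planned for all patients (a second scan, if intended, would need its own schedule entry). The price is a smaller denominator for this outcome if f > 0, for example 36 instead of 45 per arm at f = 0.2. If every patient has baseline flow, nothing changes.
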